3.3. Sample Size Considerations

Any eligible participants will be enrolled from the 2 parent Phase 3 studies, INCB 18424-306 and INCB 18424-307. The sample size is not based on any statistical power calculations.

3.4. Schedule of Assessments

Refer to Protocol Amendment 2 dated 10 NOV 2020 for a full description of all study procedures and assessment schedules (Protocol Table 3) for this study.

² Rescue treatment: If, at any time, a participant in Cohort A loses a clinically meaningful response on the face (< F-VASI75), the participant will receive open-label 1.5% BID ruxolitinib cream until Week 104 or EOT.

4. DATA HANDLING DEFINITIONS AND CONVENTIONS

4.1. Scheduled Study Evaluations and Study Periods

4.1.1. Day 1

Day 1 is the date that the first application of ruxolitinib cream or vehicle cream is administered to the participants in the extension treatment period (ie, Study INCB 18424-308).

For randomized participants not treated with any study drug, Day 1 is defined as the day of randomization.

4.1.2. Study Day

If a visit/reporting date is on or after Day 1, then the study day at the visit/reporting date will be calculated as

```
Day \# = (visit/reporting date - Day 1 date + 1).
```

If the visit/reporting date is before Day 1, then the study day at the visit/reporting date will be calculated as

Day # = (visit/reporting date - Day 1 date).

A study day of -1 indicates 1 day before Day 1.

4.1.3. Baseline Value

For randomized participants not treated with any study drug, baseline is defined as the last nonmissing assessment before or on the day of randomization for all parameters.

For participants who continue in the extension treatment period, baseline is defined as follows:

- For efficacy evaluation, baseline is the last nonmissing measurement obtained before the first application of study drug in the parent study.
- For Cohort B safety evaluation, baseline is the last nonmissing measurement obtained before or on the day of first application of ruxolitinib cream in the parent study.
- For Cohort A safety evaluation,
 - For participants who are initially randomized to receive ruxolitinib cream in the
 extension treatment period (ie, Study INCB 18424-308), baseline is the last
 nonmissing measurement obtained before the first application of ruxolitinib cream
 in the parent study.
 - For participants who are initially randomized to receive vehicle cream in the
 extension treatment period (ie, Study INCB 18424-308), baseline is the last
 nonmissing measurement obtained before the first application of vehicle cream in
 the extension period.

When scheduled assessments and unscheduled assessments occur on the same day and time of the assessment or time of first application is not available, use the following convention to determine baseline:

- If both a scheduled and an unscheduled visit are available on the day of the first application and the time is missing, use the scheduled assessment as baseline.
- If all scheduled assessments are missing on the day of the first application and an unscheduled assessment is available, use the unscheduled assessment as baseline.

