3. STUDY DESIGN

This is a Phase 3, double-blind, vehicle-controlled, randomized withdrawal and treatment extension study that will enroll eligible participants who have completed either Study INCB 18424-306 or Study INCB 18424-307 (parent studies) in which the participants will have been using ruxolitinib cream 1.5% BID for the previous 28 to 52 weeks (depending on their initial randomization in the parent study; see Figure 1).

The parent studies are randomized, vehicle-controlled studies in adolescent and adult participants (age \geq 12 years) with nonsegmental vitiligo who have depigmented areas including \geq 0.5% BSA on the face, \geq 0.5 F-VASI, \geq 3% BSA on nonfacial areas, and \geq 3 T-VASI. Total body involved vitiligo area (facial and nonfacial) was not to exceed 10% BSA. In each parent study, approximately 300 participants were to be randomized 2:1 to receive an initial, double-blind study treatment of ruxolitinib cream 1.5% BID or vehicle cream BID (applied to depigmented vitiligo areas on the face and body up to 10% total BSA) for 24 weeks. After completion of the Week 24 assessments, participants in these studies were offered the opportunity to receive an additional 28 weeks of open-label treatment extension with ruxolitinib cream 1.5% BID under the parent study protocol.

Participants who successfully completed the 52-week treatment in either of the parent studies (ie, 52 weeks of ruxolitinib cream or 24 weeks of vehicle cream plus 28 weeks of ruxolitinib cream) and tolerated ruxolitinib cream treatment without safety concern and with good compliance for continuation may be eligible to participate in this treatment extension study.

[figure not shown]
Visits in this treatment extension study are named to reflect continuation from the parent studies, with the first visit of this treatment extension study occurring at Week 52. The eligibility assessment for this extension study occurs at Week 52. The treatment extension period of this study comprises the period from the Week 52 visit to the Week 104 visit (inclusive). Following the last application of study treatment at Week 104, there will be a 30-day safety follow-up period to evaluate safety and duration of response.

Eligible participants in this study will be assigned to 1 of 2 cohorts, Cohort A or Cohort B, based on their F-VASI responses at the time of enrollment in this study (ie, at Week 52).

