8.1. General Considerations

The analyses in this section will be provided for the FAS population for each cohort. Safety data for each cohort will be summarized in separate tables.

For AEs, summary tables will be provided based on the actual treatment received as defined in Section 5.2.

For laboratory tests and vital signs, summary tables will be provided based on the actual treatment received at Week 52. For Cohort A, only assessments on or before the first dose date of open-label rescue treatment will be summarized.

Also, for safety evaluations, baseline will be defined as stated in Section 4.1.3.

Summary tables may be replaced with listings when appropriate. For instance, an AE frequency table may be replaced with a listing if it only contains a few unique PTs reported on relatively few participants.

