8.3. Clinical Laboratory Tests

8.3.1. Laboratory Value Definitions

Laboratory values and change from baseline values will be summarized descriptively by visit, and non-numeric test values will be tabulated when necessary.

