8.3.2. Laboratory Value Summaries

Clinical laboratory tests, including hematology and serum chemistry, will be performed at the Protocol-specified visits.

All test results and associated normal ranges from central laboratories will be reported in SI units. All tests with numeric values will have a unique unit per test. Any laboratory test results and associated normal ranges from local laboratories will be converted to SI units.

For test results that will be summarized with available normal ranges, the number and percentage of participants with the laboratory values being low (but never high), normal, high (but never low), and both low and high will be calculated for each test.

These shift summaries will be produced for each test for the FAS population according to the treatment groups defined for the 2 cohorts in Section 5.2. Shift tables will also be presented showing change in CTCAE grade from baseline to worst grade postbaseline. The denominator for the percentage calculation will use the number of participants in the baseline category.

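### The two randomised Cohort A arms have different safety baselines, so between-arm laboratory and vital-sign change and shift outputs carry parent-study drift from the ruxolitinib arm only

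*SAP*

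**What the plan says.** For Cohort A safety, SAP Section 4.1.3 sets the baseline by randomised arm:

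- **Ruxolitinib arm:** the last "nonmissing measurement obtained before the first application of ruxolitinib cream" in the parent study.
- **Vehicle arm:** the last "nonmissing measurement obtained before the first application of vehicle cream in" the extension, in practice the Week 52 value.

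SAP Section 3 gives the treatment already received by Week 52: "52 weeks of ruxolitinib cream or 24 weeks of vehicle cream plus 28 weeks of ruxolitinib cream". The vehicle-arm baseline is therefore an on-ruxolitinib value for everyone.

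SAP Section 8.1 carries the rule into the outputs. For laboratory tests and vital signs, "summary tables will be provided based on the actual treatment received at Week 52", and "Also, for safety evaluations, baseline will be defined as stated in Section 4.1.3". Cohort A assessments after the start of open-label rescue are left out of these summaries.

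The outputs that use this baseline are:

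- Laboratory change (Section 8.3.1): "Laboratory values and change from baseline values will be summarized descriptively by visit".
- CTCAE shifts (Section 8.3.2; Appendix A Tables 3.3.2 and 3.3.4): "Shift tables will also be presented showing change in CTCAE grade from baseline to worst grade postbaseline". The percentages take the baseline category as denominator.
- Vital-sign change and percentage change (Section 8.4).
- The change and percentage-change box plots (Appendix A, Figure 5.1.2 onward).

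Low/normal/high outputs join the list where they are laid out as shifts. Section 8.3.2 says of them "These shift summaries will be produced for each test for the FAS population according to the treatment groups defined for the 2 cohorts", and Protocol Section 10.4.2.2 plans such shift tables for parameters without a CTCAE grade.

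By-visit actual values, treatment-emergent adverse events and efficacy do not use the arm-specific baseline.

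**The concern.** Cohort A is the only randomised comparison in the study. Because randomisation takes place at Week 52, the two arms have the same expected history up to that point. A change score taken from different points in that history puts part of it into one column and not the other. The ruxolitinib column then shows parent-period change plus extension change, while the vehicle column shows extension change only.

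Someone reading the columns side by side would attribute the whole gap to continuing rather than stopping ruxolitinib. SAP Section 8.2.2 names cytopenias, thrombocytosis and liver test elevations as events of interest, so these are tables that will be read closely. Neither document plans a common-baseline version or warns against comparing the columns. Protocol Sections 10.4.2.2 and 10.4.2.3 say only baseline, and SAP Section 10.1 does not mention the arm-specific rule.

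**Working it through.** The documents give no figure to reproduce here. The check is time arithmetic plus an identity, followed by an illustration on assumed values.

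**1. Time from baseline to the same visit.** The inputs are the treatment periods in SAP Section 3. First ruxolitinib is at Week 0 for participants originally on ruxolitinib and after Week 24 for those originally on vehicle. The extension starts at Week 52. For visit week w, the span is w − 0 or w − 24 in the ruxolitinib arm and w − 52 in the vehicle arm.

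| Visit | Ruxolitinib arm, originally ruxolitinib | Ruxolitinib arm, originally vehicle | Vehicle arm |
|---|---|---|---|
| Week 56 | 56 | 32 | 4 |
| Week 80 | 80 | 56 | 28 |
| Week 104 | 104 | 80 | 52 |

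**2. Offset in mean change.** Let μ be the pre-ruxolitinib mean and μ + d the Week 52 mean, equal in expectation in both arms by randomisation. At an extension visit, before post-rescue exclusions, take the ruxolitinib arm as still at μ + d and the vehicle arm at μ + d(1 − r), where r is the share of d that recovers off drug.

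- SAP baselines: ruxolitinib change = d; vehicle change = −r·d; difference = d(1 + r).
- Common Week 52 baseline: 0 − (−r·d) = r·d.
- Actual values: (μ + d) − (μ + d(1 − r)) = r·d.
- Offset: d(1 + r) − r·d = d, for every r.

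The assumption that the ruxolitinib arm stays level is not needed. For any extension means R and V, (R − μ) − (V − (μ + d)) = (R − V) + d.

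**3. Illustration for assumed d, in SD units.** Each cell gives the difference with SAP baselines, then with a common Week 52 baseline.

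| d | r = 0 | r = 0.5 | r = 1 |
|---|---|---|---|
| 0 | 0; 0 | 0; 0 | 0; 0 |
| 0.10 | 0.10; 0 | 0.15; 0.05 | 0.20; 0.10 |
| 0.25 | 0.25; 0 | 0.375; 0.125 | 0.50; 0.25 |
| 0.50 | 0.50; 0 | 0.75; 0.25 | 1.00; 0.50 |

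A simulation of 400,000 participants allocated 1:1, with assumed within-person correlation 0.7, agreed with these values to within about 0.005 SD.

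**4. Shift tables.** This simulation assumes a low limit at the 5th percentile of the pre-ruxolitinib distribution, the seven extension treatment visits (Weeks 56, 60, 64, 68, 80, 92 and 104), correlation 0.7, and the same true course in both arms. Entries are the probability of a shift from normal. With a common Week 52 baseline, both arms would take the vehicle-arm value.

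| d (SD) | Ruxolitinib arm | Vehicle arm | Ruxolitinib arm if 4 parent visits also count |
|---|---|---|---|
| 0 | 0.125 | 0.124 | 0.158 |
| −0.10 | 0.151 | 0.145 | 0.189 |
| −0.25 | 0.199 | 0.180 | 0.243 |
| −0.50 | 0.294 | 0.247 | 0.346 |

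The SAP does not say whether parent visits after the ruxolitinib-arm baseline count as postbaseline. If they do (four is an assumed number), that arm has more chances to reach a worst grade, and the arms differ even when d = 0.

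**The case against.** The strongest reply has five parts.

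- **The tables are descriptive.** SAP Section 3.2 calls all analyses exploratory, and no between-arm difference, interval or test is planned for laboratory or vital-sign data. This stands and limits the weight of the point. Columns placed side by side are still the way such safety data are compared.
- **Actual values already give the contrast for means.** As step 2 shows, their difference equals the common-baseline result. This largely stands. It does not cover grades: the protocol's worst-grade summary that ignores baseline (Section 10.4.2.2) is not named in SAP Section 8.3.2 or among Appendix A Tables 3.3.1 to 3.3.4. Appendix A calls its lists guidelines, so that summary may yet be produced. As listed, a reader would have to add counts across the baseline rows of the shift tables.
- **The split is deliberate.** Each arm is measured from before the treatment it receives in the extension, and Cohort B follows the same logic. For describing long-term exposure within the ruxolitinib arm this is sensible, and a Week 52 baseline alone would hide cumulative change. That is a reason to keep the rule for that purpose, not to use it for comparing arms.
- **d is probably small.** Protocol Section 2.3 describes the Phase 2 hematology changes as minor, transient and not clinically significant. This is a fair expectation, but no value is given.
- **A common baseline would not fully restore the randomised comparison.** Dropping post-rescue assessments makes later visits selective whatever the baseline. This is true, but it leaves the added offset where it is.

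**Conclusion.** The concern holds. In the Cohort A change outputs, the between-arm difference in means is offset by exactly d, whatever happens after Week 52. Percentage-change and shift outputs inherit the same asymmetry, and in the shift tables the rows and denominators also depend on arm.

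The identity rests only on the two arms having equal expected means up to Week 52, which randomisation supplies. Post-rescue exclusions can disturb it at later visits. The size of d is unknown and there is no mean offset if it is zero. It is itself a mix of a 52-week and a 28-week shift, weighted by the share of Cohort A originally on vehicle, which the documents do not give. The low/normal/high outputs are affected only if they are laid out as shifts.

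No formal test, efficacy result or adverse-event table depends on this. It should be corrected because the misreading is avoidable at little cost.

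**What to change.** For Cohort A between-arm change, percentage-change and shift outputs (CTCAE and any low/normal/high shifts), define one baseline for both arms: the last nonmissing value before the first study-drug application in Study INCB 18424-308, in practice Week 52. State that only extension visits count as postbaseline in these outputs. Keep the pre-ruxolitinib baseline for the ruxolitinib arm in a separate summary labelled as long-term exposure.

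The cost is SAP wording in Sections 4.1.3 and 8.1, one derived baseline flag and one extra set of descriptive tables. No new data are needed, because Protocol Table 3 already schedules hematology, chemistry and vital signs at Week 52.

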4.1.4. Handling of Missing and Incomplete Data

For the primary and key secondary endpoints, which are durations of responses, the algorithm in Table 2 will be applied to determine censoring or event.

Table 2: Algorithm for Censoring

| Situation | Date of Relapse/Lost Response or Censoring | Outcome |
|---|---|------------------------|
| Relapse/lost response documented on or between scheduled visits | Date of relapse/lost response | Relapsed/lost response |
| No relapse/maintain response | Date of last assessment | Censored |
| Treatment discontinuation | Date of last assessment | Censored |
| Applying rescue treatment (1.5% BID) in extension treatment period without relapse/lost response status | Date of rescue treatment | Censored |

For all other endpoints, no imputation will be performed for missing values unless otherwise specified.

4.2. Variable Definitions

4.2.1. Body Mass Index

Body mass index will be calculated as follows:

BMI $(kg/m^2) = (weight ([kg])/(height [m])^2$.

4.2.2. Concomitant Medication

Concomitant medication is defined as any nonstudy medication that is started accordingly:

- Before the date of first application of study drug in Study INCB 18424-308 and is ongoing throughout the study or ends on/after the date of first application of study treatment.
- On/after the date of first application of study drug in Study INCB 18424-308 and is ongoing or ends during the course of study treatment.

A concomitant medication could also be classified as "both prior and concomitant medication" if the end date is on or after the first application of study drug. In the listing, it will be indicated whether a medication is prior only, concomitant only, or both prior and concomitant. For the purposes of analysis, all medications will be considered concomitant medications unless the medications can unequivocally be defined as not concomitant.

5. STATISTICAL METHODOLOGY

5.1. General Methodology

Unless otherwise noted, SAS® software (SAS Institute Inc, Cary, NC; v9.1 or later) will be used for the generation of all tables, graphs, and statistical analyses. Descriptive summaries for continuous variables will include, but not be limited to, the number of observations, mean, standard deviation, median, minimum, maximum, first quartile, third quartile, and 95% CI. Descriptive summaries for categorical variables will include the number and percentage of participants in each category.

5.2. Treatment Groups

This is a double-blind, vehicle-controlled, randomized withdrawal and treatment extension study that will enroll eligible participants who have completed either Study INCB 18424-306 or Study INCB 18424-307 (parent studies). Data will be summarized based on the treatment regimen that was assigned at Week 52 (ITT-Ext) or that the participant actually applied (FAS).

For Cohort A, treatment groups are ruxolitinib cream 1.5% BID and vehicle cream for participants before open-label rescue treatment. For participants who cross over from vehicle cream to open-label ruxolitinib cream, the treatment group will be Vehicle-1.5% BID. For Cohort B, the treatment group will be based on the treatment assignment at Day 1 of the parent study (vehicle to 1.5% BID and 1.5% BID to 1.5% BID).

5.3. Analysis Populations

The data from participants at Site 710 were removed from all efficacy analyses performed on the ITT-Ext population and FAS owing to noncompliance with the Protocol in the parent study resulting in serious concerns with the data quality.

5.3.1. Full Analysis Set

All participants enrolled in the study who applied study drug (ruxolitinib cream or vehicle) at least once at or after Week 52 for each cohort (FAS Cohort A and FAS Cohort B) will constitute the FAS.

The FAS will be used for the summary of analyses of demographics, baseline characteristics, participant disposition, efficacy, and safety data.

5.3.2. Intent-to-Treat in Long-term Extension

All participants who achieved ≥ F-VASI90 at Week 52 will be randomized into Cohort A and will constitute the ITT-Ext population. Treatment groups for this population will be defined according to the treatment assignment at the time of randomization regardless of the actual study medication the participant might take during the study.

5.3.3. Relapse Evaluable Set

All participants who are in the ITT-Ext population, experience relapse (defined as < F-VASI75), and receive open-label rescue treatment will constitute the RES.

5.3.4. Pharmacokinetic Evaluable Population

The PK evaluable population will include all participants who applied ruxolitinib cream at least once and provided at least 1 blood sample (1 PK measurement) that complies with the instructions in the Protocol. The study pharmacokineticist will review data listings of study drug application and sample records to identify participants to be excluded from PK data analyses. The study research investigator will review data listings of data and sample records to identify participants to be excluded from analyses of data.

6. BASELINE, EXPOSURE, AND DISPOSITION

Appendix A provides a list of planned tables, figures, and listings. Sample data displays are included in a separate document.

6.1. Baseline, Demographics, and Disease History

6.1.1. Demographics

The following demographics will be summarized for the FAS population for each cohort by treatment group: age, age group (< 18 years, 18 to < 65 years, \geq 65 years; < 18 years, \geq 18 years), sex, race, ethnicity, region, weight, height, and BMI.

6.1.2. Baseline Disease Characteristics

Baseline disease characteristics summarized for the FAS population include but are not limited to the following:

- Time since initial diagnosis of vitiligo
- Vitiligo diagnosed in childhood (No/Yes [age]: 0-5 years, 6-11 years, 12-17 years)
- Disease status (stable/progressive)
- Skin type (Type I/II/III/IV/V/VI)
- Other autoimmune disorders
- Prior therapy for vitiligo (predefined systemic treatments, phototherapy, and surgical procedures)
- History of acne vulgaris (No/Yes)
- Currently have acne vulgaris on the face (No/Yes)
- Vitiligo in genital area (No/Yes)
- Baseline F-VASI score
- Baseline T-VASI score

- Baseline F-BSA involvement (% of the total body)
- Baseline T-BSA involvement (% of the total body)

6.2. Disposition of Participants

The number and percentage of participants who were randomized, treated, and completed the extension treatment period will be summarized by treatment groups for each cohort. Moreover, participants who discontinued the treatment or withdrew from the study during the extension treatment period with a primary reason for discontinuation will also be summarized.

6.3. Protocol Deviations

Protocol deviations will be summarized by treatment groups for each cohort.

6.4. Exposure

A summary for overall exposure within this study will be provided for the FAS for each cohort. For Cohort A, a summary will be provided based on the actual treatment received as defined in Section 5.2.

6.5. Study Drug Compliance

Overall compliance (%) for the application of ruxolitinib cream or vehicle cream will be calculated for all participants based on the actual treatment received in the FAS population as follows:

Overall application compliance (%) = $100 \times [\text{total number of nonmissing applications}]/[\text{total number of intended applications}]$

where the total number of nonmissing applications is the total number of applications that the participant actually applied during the study. The total number of intended applications is the number of planned applications minus the number of interrupted applications.

